Given the above-mentioned background, the following study has been designed to evaluate the arrest of myopia progression with the daily use of nationally designed glasses, comparing such progression with a virtual control group of similar age in a population of myopic children and adolescents of the same environment in our country.

WORKING HYPOTHESIS

The nationally designed lenses can be as effective as the proven international industry designs that have been subjected to controlled trials against natural history of the disease.

PURPOSE

To treat a group of consecutive volunteer patients who choose between the affordable treatment in our environment (daily diluted atropine drops for several years) or the special lenses for myopia control designed by the National Industry. The purpose is to compare the progression during one year with the national lenses with respect to the progression with the foreign lenses and/or with the natural history of a virtual control group.

OBJECTIVES

Primary

To assess whether the intervention with locally designed spectacles is well tolerated and adhered to with daily use in childhood and adolescence.

Secondarily

To assess whether intervention with locally designed glasses can control myopia progression in childhood and adolescence.

DEFOCUS GLASSES OF NATIONAL DESIGN

The design of the national defocus lens is based on the original design presented by Carly Lam,⁴⁰ with a 9 mm central zone for distance correction and a correction ring with a +3.50 dioptre defocus between 9 and 32 mm in diameter to act in principle on the para foveal zone which is the one that detects the defocus that governs the growth of the eye.⁴¹ Instead of peripheral defocusing micro lenses that do not alter the visual field in the area of the 32

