All the data of affiliation, contact telephone number, date of birth, refraction under cycloplegia, axillary length and questionnaire will be entered in a centralized digital history by NOVAR developers. These data will be kept confidential. During follow-up visits, accredited professionals throughout the country will have access to upload the data required for each visit. One month after the eyeglasses are delivered, the professional will conduct a telephone survey to parents to evaluate adherence. The first stage of the study will be completed after one year and the child will be able to continue with the treatment for myopia control according to the consensus guidelines on myopia treatment of the Myopia Study Group of the SAOI (Annex I). For virtual control group, data will be taken from 114 children followed with cycloplegia by the pandemic study group during the years 2018-2019 that showed for an average age of 12 years an annual pre-pandemic progression of -0.45 D. In the present study, We expect to evaluate the progression with peripheral defocus treatment over one year of an equivalent group of children.

WORK PLANNING / GANTT CHART:

Activity	TIME IN MONTHS						
	1	2-4	5-24	25	26	27	28
Project Design	X	X					
Bibliographic search	X			X	X		
Ethics Committee Presentation		X					
Data collection			X				
Data analysis				X	X		
Preliminary results					X	X	
Final Results						X	X
Report writing							X

INCLUSION / EXCLUSION CRITERIA

All consecutive patients of both genders who freely opt for lenses of national industry will be included in the present study. All patients who present any systemic or ocular pathology that may affect their refraction measurements or their evolution will be excluded from the study. Also excluded from the protocol in the follow-up will be those patients who, even using defocus glasses, had in 6 months an improvement equal to that expected without any intervention. These patients will be treated with other options available in our environment at the time of the change. The computerized medical records system will be configured to detect such patients at the time of loading the follow-up data and will send an alert to the investigators.

EVALUATION OF TOLERANCE AND ADHERENCE

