Adherence will be evaluated at the one-year follow-up and will be reported as the number of cases that failed to complete the three scheduled visits in one year with respect to the total number of cases that were enrolled in compliance with the first visit and the delivery of the spectacle. Tolerance of these glasses will be assessed with a tolerance questionnaire that is presented in the attached medical record. This questionnaire has already been tested on 24 subjects aged 18 to 24 years in a pilot trial presented at the International Myopia Conference, as explained in the previous section on the defocus spectacle, showing good tolerance in these subjects. Some tests in younger children that were performed in the last months show that tolerance is very good in them, since minors have greater plasticity and adaptability than young adults previously tested. Tolerance and adherence will be classified as GOOD / BAD, in a dichotomous way, with the cut-off according to the answer given by whether the child tolerated them well or not. On the other hand, tolerance will also be evaluated in dichotomous form with responses to reading and walking

performance.

PROCEDURES TO GUARANTEE ETHICAL ASPECTS

The anonymity of all participants will be preserved. Patients' names will be removed from the database for statistical analysis. The only ones who will know the names of the patients are the physicians involved in their primary care, and they will have to keep the information in their respective institutional medical records and enter the data necessary for the research in a web form designed by the sponsoring company.

The Declaration of Helsinki and its modifications, the Good Clinical Practices guide, the harmonization norms and the resolution of the Ministry of Health 1480/11 will be observed and taken into account as guidelines (See informed consent ANNEX VI). It is stated for the record that the principal investigator does not have any type of conflict of interest since the patenting of the defocus glasses is the responsibility of the sponsor's company.

SAFETY PRECAUTIONS

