One month after the delivery of the spectacle, the principal investigator in charge will make a telephone call to the parent of the study subject conducting the tolerance survey and thus verifying adherence to spectacle use. The survey is detailed in the attached medical record and responses will be uploaded into the computerised web-based system that will be developed for this study. The system will automate the alerts for these safety calls with automatic emails sent to the principal investigator in the month of spectacle delivery.

PLAN FOR ANALYSING THE RESULTS

The results of numerical variables shall be expressed as mean and standard deviation or median and interquartile range according to whether they are normally or skewed. Nominal variables will be expressed as absolute frequency and percentage. For the comparison of numerical variables, Student's t-test or Mann Whitney U-test will be used as appropriate. Nominal variables will be compared using the Chi-square test or Fisher's exact test as appropriate. A p-value of $p \leq 0,05$.

HUMAN RESOURCES

[name] and [name] are in charge of the design and control of the research. Statistical analysis will be performed by [name]. Physicians accredited to treat patients will have to demonstrate the ability to perform routine consultations for myopia control, refraction studies under cycloplegia and optical biometry. Once accredited, they will have a username and password to upload their data into the web form. Accredited doctors will be in permanent communication with doctors [name] and [name]. There will be a myopia progression monitoring system within the computerised system that will send reports if any child progresses more than 0.25 dioptres in six months to alert researchers so that precautionary measures can be taken in such cases.

MATERIAL RESOURCES

Optotypes, Retinoscope, Autorefractometer and Biometer posters of accredited institutions.

Approximately four institutions with a high turnover of paediatric consultations are expected to be accredited for an estimated enrolment time of 6 months.

Peripheral defocus spectacles will be provided by the sponsor (NOVAR) free of charge to all study subjects for one calendar year with the possibility of extending the study for two years. At the end of the study, if the expected positive results are found, the glasses will remain in the possession of the study subjects.

FINANCIAL RESOURCES

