Do you take tutoring outside of school? (Circle) YES NO

How many hours do you spend outdoors when you leave school?Hs

How many hours per day do you spend reading books or doing homework?
.....Hs

How much time per day do you spend playing with your cell phone or tablet?
.....Hs

ON ANY SATURDAY OR SUNDAY.....

How many hours per day do you spend reading books or doing homework?Hs

How many hours per day do you spend outdoors on a weekend day?Hs

How much time per day do you spend playing with your cell phone or tablet?
.....Hs

PART II EYEGLASS DELIVERY

DATE

PART II. BIS (ATTACHMENT QUESTIONNAIRE)
AT THE MONTH OF DEFOCUS EYEWEAR DELIVERY (TELEPHONE SURVEY)
DATE

Have you worn the glasses at home during this month? YES NO

Have you worn glasses all day this month? YES NO

If you answered "YES" to any of the above, continue with these

In general, do you tolerate them well? YES NO

Have you ever had trouble turning your head to look sideways? YES NO

Out of the seven days of the week, how many days do you not use them?.....

Have you ever had trouble turning your head to look down when reading? YES NO

Have you ever had trouble turning your head to look down when walking? YES NO

PART III

DATE SECOND VISIT AFTER SIX MONTHS.....

EYE DER SPHERICALCILINDRICAL AXIS.....

SPHERIC IZQ EYE.....CILINDRITRIC AXIS.....

AXIAL LENGTH OD..... OI.....

PART III (BIS) SIX MONTH ADHERENCE QUESTIONNAIRE

Have you worn your glasses at home during this month? YES NO

Have you worn glasses all day during this month? YES NO

If you answered "YES" to any of the above continue with these.....

In general, do you tolerate them well?

YES NO

Have you found it difficult to turn your head to look sideways? YES NO

Of the seven days of the week, how many days do you not use them?

Did you have trouble turning your head to look down when reading? YES NO

Have you had trouble turning your head to look down when walking? YES NO

PART IV

DATE THIRD VISIT AT TWELVE MONTHS.....

RIGHT EYE SPHERICALCILINDRICAL AXIS.....

LEFT EYE SPHERICAL.....CYLINDRICALAXIS.....

AXIAL LENGTH OD..... OI.....

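### The one-month tolerance survey is addressed to the parent, the six-month form names no respondent, and neither form records who answered a primary-objective measure

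*Combined protocol and SAP*

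**What the plan says.** The primary objective, under Objectives, is "To assess whether the intervention with locally designed spectacles is well tolerated and adhered to with daily use in childhood and adolescence".

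Two sections describe the month-1 contact. Methods says that "the professional will conduct a telephone survey to parents to evaluate adherence". Safety Precautions is the more relevant passage because it names tolerance: the principal investigator "will make a telephone call to the parent of the study subject conducting the tolerance survey and thus verifying adherence to spectacle use".

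Evaluation of Tolerance and Adherence sets the scoring. Tolerance and adherence are classed GOOD or BAD, "with the cut-off according to the answer given by whether the child tolerated them well or not". In addition, "tolerance will also be evaluated in dichotomous form with responses to reading and walking" performance. On the instrument's history the same section says: "This questionnaire has already been tested on 24 subjects aged 18 to 24 years in a pilot trial". It then reports very good tolerance in recent tests in younger children.

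The attached medical record holds the questions. Part II bis (month 1, by telephone) asks about general tolerance, turning the head to look sideways, looking down when reading, looking down when walking, and days per week without the glasses. Part III bis (six months) repeats these items but states neither who answers nor how. Part IV (twelve months), as shown, lists refraction and axial length only.

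**The concern.** Apart from days of use, the items ask what it is like to look through the lens. The child has that experience; a parent knows it only by watching or being told. The plan nevertheless addresses the month-1 tolerance survey to the parent and takes the class from the answer received.

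As the forms stand, month 1 and month 6 are the only two tolerance readings. The first is addressed to the parent. The second belongs to a visit that the child attends for refraction and biometry, so the child may well answer there, but nothing says so. With no respondent field, an analyst could not tell self-report from proxy report at either time, and could not check afterwards whether it mattered.

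The items also target the difficulties that the plan itself anticipates. Defocus Glasses of National Design reports that pilot wearers had trouble walking about and read with small sideways head movements. Safety Precautions treats the month-1 call as a safety contact as well, so a walking difficulty that the parent does not know of would escape both uses of the call.

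**Working it through.** **Who answers, by source**

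| Source | Time | Addressed to | Respondent recorded? |
|---|---|---|---|
| Methods | month 1 | parents, for adherence | no |
| Safety Precautions | month 1 | parent, for tolerance and adherence | no |
| Form, Part II bis | month 1 | not named; items in the second person | no |
| Form, Part III bis | month 6 | not named; items in the second person | no |

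The second-person wording does not settle the matter. The baseline form in the same record speaks to the parent about the child and then moves to the second person for questions about the child's tutoring and outdoor time. The only explicit statements of respondent are the two that name the parent.

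**Which answer classifies.** The scoring rule refers to the answer given, but no section says whether month 1 or month 6 sets the class. Plan for Analysing the Results lists generic tests and no comparison of tolerance between the two times.

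**Size, as illustration.** The plan gives no parent-child agreement rate and no target for tolerance. Its only sample-size calculation concerns progression and does not bear on this point. Let

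- t = true proportion tolerating. I use 70%, the pilot figure for good reading tolerance in 17 respondents (Defocus Glasses of National Design);
- m = share of truly intolerant children whose trouble the parent does not report (assumed);
- f = share of truly tolerant children whom the parent reports as BAD (assumed).

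Observed GOOD = t(1 − f) + (1 − t)m.

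With f = 0:

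- m = 10%: 0.70 + 0.30 × 0.10 = 73%
- m = 30%: 0.70 + 0.30 × 0.30 = 79%
- m = 50%: 0.70 + 0.30 × 0.50 = 85%

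The 10-30% range shifts GOOD by 3 to 9 points, or 1.5 to 4.5 of the 50 planned children. For other true rates, the same range gives 64-72% at t = 60% and 82-86% at t = 80%.

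With f = 5%, GOOD falls by 0.70 × 0.05 = 3.5 points, giving 69.5% at m = 10% and 75.5% at m = 30%. The two errors cancel when 0.70f = 0.30m, that is f = 4.3% for m = 10% and f = 12.9% for m = 30%.

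**Against sampling error.** The 95% Wilson interval for 35 of 50 (70%) is 56% to 81%, a half-width of about 12 points. A shift of 3 to 9 points lies within it. Only the m = 50% case (15 points) exceeds it. Unlike sampling error, however, a reporting bias would not shrink with more children.

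**The case against.** Four counter-arguments deserve weight.

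1. **The child is not barred from answering.** The items are worded as if to the wearer, the scoring rule speaks of the child's tolerance, and calling a minor's parent does not prevent the child from coming to the phone or the parent from relaying an answer. This stands. A reader might infer that the plan excludes the child; it does not. What it does is name the parent as the person surveyed and require nothing of the child.

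2. **The direction of error is not established.** A reader might infer that parent report inflates GOOD by a known amount. No section supports that. Parents may miss trouble, but they may also over-report it, for instance on seeing the glasses taken off, and the plan has the glasses worn mainly at home, where parents can observe. This stands, and it reduces the percentages above to an illustration.

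3. **The questionnaire's history is not confined to adults.** A reader might infer that it was tested only in subjects aged 18 to 24. The next sentence mentions tests in younger children. It does not say which instrument was used or who answered, so it neither shows nor rules out testing in this age group. No parent-answered version is described.

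4. **No planned analysis compares month 1 with month 6.** This stands. The change of respondent does not corrupt a specified test. It leaves two readings of one primary-objective measure that may not be comparable, with no rule on which one classifies.

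A parent is a reasonable informant on adherence, so the sentence in Methods, taken alone, is not objectionable. The weight rests on Safety Precautions.

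**Conclusion.** The point holds in a limited form. The month-1 survey of a primary-objective measure is addressed to a proxy, although its tolerance items concern the wearer's own experience. The month-6 respondent is unstated, and neither form records who answered. Tolerance may therefore rest on parent report at one time and child report at the other. Trouble unknown to the parent could be scored GOOD.

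The size and net direction of the resulting error cannot be derived from the documents. The shift from 70% to 73-79% depends on an assumed 10-30% of trouble going unreported and on no false BAD answers; modest over-reporting removes the lower end of it. It should not be cited as an estimate of bias. The case for change rests on the plan's own wording and on the very small cost of repair, not on a demonstrated distortion. Confidence is medium.

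**What to change.** - In Safety Precautions, have the child answer the general tolerance, sideways, reading and walking items, with the parent on the line. Align the sentence in Methods.
- Apply the same rule at six months, with the parent present. The parent may answer days of use at both times.
- Add a field for who answered to Part II bis and Part III bis.
- In Evaluation of Tolerance and Adherence, base GOOD/BAD on the child's answer at one time point stated in advance, and report the other time point separately.

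The cost is a few sentences, one field on each of two forms and a slightly longer call. The youngest children may need items repeated. No extra visit is needed.

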Due to the problem of attrition in the control group, it has been suggested in the last International Myopia Conference that controlled field studies be performed by a virtual group, without performing a non-inferiority study, since atropine 0.01% could not be taken as gold standard because it is not yet approved and as we said, it is off-label in Argentina. Data on progression in Asia or Europe could be used for this virtual control group, but it would be more convenient to have a virtual control group in one's own living environment. In the case of our country there is already a possible control group of 114 children of 12 years of age on average who were followed up with cycloplegia during the years pre-pandemic and from which it is known that the progression was from 0.43+/-0.52 diopters in one year.³⁶

It is thus proposed to perform a prospective clinical study in 100 children who will be enrolled when in the usual consultation for their eyeglasses control they can choose to do the treatment accessible in our environment (the diluted atropine drop) or a treatment that is possibly equally effective with special glasses designed in our environment. It is

expected that there will be similarity of effect on progression because the lens is based on the principles of defocusing of eyeglasses and contact lenses already proven by the international industry.³⁷ Our lens has the characteristic of being much simpler in its carving and construction, making it more economical for our environment where it has already been presented from the theoretical point of view.³⁸

Moreover, the special myopia control spectacle lacks the possible toxic effects of a drop instilled in the eye for many years until emerging adulthood. In addition, to avoid including children who may have rapid progressions to high myopia, treatment will be offered only to children over 8 years of age. In our environment, where children are outdoors a lot, the progression is slower than in Asian countries and is around -0.50 diopters per year, as we said.³⁶ A strong myopia is the one that exceeds -5.00 diopters.³⁹ Thus the risk for a child included in this project is to progress -0.25 diopters in six months (the resolution limit of the measurement method), so each child who does not respond well with arrest of progression at six months may be removed from the protocol and switched to atropine treatment.

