agree to take the test for one year, with no ocular pathology other than myopia, with spherical equivalent (sphere + 50% of the cylinder) between -0.50 D and -5.00 D, with astigmatism less than -2.00 D in each eye, with anisometropia less than -1.00 D, with keratometry less than 47.00 D in the most curved meridian. Genetic syndromes will not be included or ruled out. A complete ophthalmologic evaluation will be performed including tonometry, fundus, subjective refraction and refraction under cycloplegia with two drops of 1% cyclopentolate instilled 5' apart and performed 40' after the last drop. Visual acuities of the subjective refraction will be greater than 8/10 in each eye. Axillary length measurements with optical biometry will be performed at the beginning of treatment at follow-up and at the end of the study. New cycloplegic refractions will be performed during follow-up and at one year of treatment. A survey of habits and history, including reading, outdoors, ON-OFF contrast use, hours of schooling, age of onset of spectacle use and family history of high myopia (also likely use of devices to monitor these habits in selected group) will be conducted. A pair of spectacles and their frames will be provided free of charge to all children studied for one year with the special addendum of peripheral defocus treatment or laser treatment for contrast reduction depending on the treated group. The children will be instructed to wear the glasses especially in front of smartphones, tablets, PC's or books at home after five o'clock in the afternoon and until going to bed, every day of the week including Saturdays and Sundays. During the rest of the day they will use their usual correction without properly updated defocus. As defocus in experimental animals has more effect in stopping experimental myopia in the afternoon than in the morning,⁴⁴ It is expected that use in the afternoon only will be sufficient to achieve the effect. On the other hand, the peripheral contrast-lowering lens that has shown good tolerance and absence of visual field alteration will be used all day long by the subjects under treatment.

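### The entry limits set for the lens group are not applied to the 114 historical controls, whose own selection criteria are not stated, so the efficacy comparison may be biased in either direction

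*Combined protocol and SAP*

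**What the plan says.** **Lens group.** METHODS and the later CRITERIA FOR INCLUSION restrict age, refraction, astigmatism and acuity. METHODS adds further limits: "with astigmatism less than -2.00 D in each eye, with anisometropia less than -1.00 D, with keratometry less than 47.00 D". INCLUSION / EXCLUSION CRITERIA adds: "All patients who present any systemic or ocular pathology that may affect their refraction measurements or their evolution will be excluded from the study". CURRENT STATE OF RESEARCH gives the reason for the lower age limit: "to avoid including children who may have rapid progressions to high myopia, treatment will be offered only to children over 8 years of age".

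**Controls.** METHODS says "data will be taken from 114 children followed with cycloplegia by the pandemic study group during the years 2018-2019", with an average age of 12 years. CURRENT STATE OF RESEARCH describes the aim as "comparing such progression with a virtual control group of similar age", in myopic children and adolescents from the same setting. METHODS expects to measure progression "over one year of an equivalent group of children". No age range, refractive range or selection criteria are given for the 114, and no subset or matching is planned.

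**Analysis.** PLAN FOR ANALYSING THE RESULTS offers Student's t-test or the Mann-Whitney test for numerical variables, at p ≤ 0.05, without covariates.

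**The concern.** With an external control, the two groups are comparable only as far as the same eligibility rules define both. Here one group is filtered on several characteristics, and the plan does not say whether the other was filtered at all.

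The protocol itself treats one of these characteristics as prognostic. PROBLEM STATEMENT JUSTIFYING THE STUDY says progression is slower above age 8 and slows further with age, and the lower age limit was chosen to leave out fast progressors. INCLUSION / EXCLUSION CRITERIA also removes conditions that could alter how refraction evolves. If the 114 include children the trial would not admit, the difference in mean progression mixes a lens effect with a difference in who was followed.

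Controls outside the limits have no counterpart in the lens group. A regression could account for them only by extrapolation, and none is planned.

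At stake is the efficacy conclusion. OBJECTIVES ranks efficacy second, but PURPOSE is framed as a comparison of progression and SAMPLE AND SAMPLE SIZE is built on it. The primary objective, tolerance and adherence, does not use these controls.

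**Working it through.** **1. The plan's own figure.** SAMPLE AND SAMPLE SIZE gives n = 31 for a difference of 0.25 D and an SD of 0.50 D. Assuming two-sided 5% and 80% power (neither is stated), a one-sample formula gives (0.50 × (1.96 + 0.84) / 0.25)² = 31.4, which reproduces it. Then 31 × 1.2 = 37.2, rounded up to 38. The figure therefore fits a calculation that takes the control mean as a fixed benchmark, which makes it important which children that mean describes.

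**2. Inputs.**
- Lens completers: 50 less the plan's 20% loss = 40, SD 0.50 D.
- Controls: 114. CURRENT STATE OF RESEARCH says "the progression was from 0.43+/-0.52 diopters in one year"; METHODS says "an annual pre-pandemic progression of -0.45 D". I use 0.43 D and SD 0.52 D, the pair that comes with an SD.
- Assumed, not in the documents: a share f of the 114 is ineligible and progresses at r D/year.

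**3. Standard error.** SE = √(0.50²/40 + 0.52²/114) = √(0.00625 + 0.00237) = 0.093 D.

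**4. Bias for an inert lens.** The eligible controls average (0.43 − f·r)/(1 − f). An inert lens group should progress at that rate, so its apparent gain is b = 0.43 minus that average. The chance of a significant result favouring the lens is 1 − Φ(1.96 − b/SE), which is 2.5% when b = 0.

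| f | r (D/year) | Eligible mean (D) | b (D) | b / 0.43 | False win |
|---|---|---|---|---|---|
| 10% | 0.6 | 0.411 | 0.019 | 4% | 4% |
| 20% | 0.6 | 0.388 | 0.043 | 10% | about 7% |
| 10% | 0.8 | 0.389 | 0.041 | 10% | 6.5% |
| 20% | 0.8 | 0.338 | 0.093 | 22% | 17% |

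With 0.45 D in place of 0.43 D, b runs from 0.017 to 0.088 D.

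**5. The other direction.** Take b = −0.10 D as an illustration, with ineligible controls progressing more slowly. A false win falls to 1 − Φ(1.96 + 0.10/0.093), about 0.1%. For a true effect of 0.25 D, the chance of detecting it falls from Φ(0.25/0.093 − 1.96), about 77%, to Φ(0.15/0.093 − 1.96), about 37%.

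**6. What a typical significant result would need.** 1.96 × 0.093 = 0.18 D of imbalance. The largest bias in the table is 0.093 D, about half of that.

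**7. What the documents say about direction.**
- Controls below the lower age limit: faster progression is expected, which favours the lens.
- Controls above the upper age limit: slower progression is expected, which counts against the lens.
- Pathology: excluded because it may alter evolution; no direction is given.
- Refraction, astigmatism, anisometropia, keratometry and acuity: the documents do not say how being outside these limits relates to the yearly rate of progression.

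**The case against.** The strongest reply is that the gap is one of silence. The source study's criteria lie in a cited paper that is not part of these documents, and all 114 may already meet similar limits. The protocol does intend similarity in age, condition and setting. The single control mean in METHODS reports an earlier result; the text does not say that only this mean will be used. **This stands** against any claim that the controls lack the limits. It does not remove the point, because similar age and equivalence are stated as aims, with no rule to reach them, and a shared average age does not establish a shared range.

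Second, a reader might infer that the entry criteria by themselves would make an inert lens look effective. The documents do not support this. They give a direction only for age, and age can act both ways. The shares and rates in the table are assumptions, and even the harshest row gives about half the imbalance needed for a typical significant result.

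Third, the filter cannot be run as the protocol stands, because the entry limits contradict each other and access to individual control records is implied but not confirmed. **This stands**, and the fix allows for it.

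Fourth, the point overlaps with adjustment or matching. Matching on age and refraction would also drop controls without counterparts on those variables. The overlap is partial: matching on those two would not apply the astigmatism, anisometropia, keratometry, acuity or pathology limits, and filtering does not balance age and refraction within the limits.

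**Conclusion.** The point holds as a gap in the plan that can bias the efficacy comparison, not as a demonstrated bias. Limits are set for one group and are not applied to the other, the other group's selection is unreported, and the test is unadjusted.

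The direction is document-supported only for age: towards the lens for controls below the lower limit, against it for controls above the upper limit. The 0.02-0.09 D range and the 4-17% false-win rate rest on the assumed 10-20% ineligible share and 0.6-0.8 D/year, with 40 completers against 114 controls. If all 114 qualify, this source of bias is zero. If the ineligible controls progressed more slowly, a real effect could be missed.

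The change should be made, but because efficacy is a secondary objective the point does not undermine the whole study.

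**What to change.** 1. Reconcile the entry limits first. Age is 8-15 years in METHODS but 8-16 in POPULATION and CRITERIA FOR INCLUSION. Refraction is −0.50 to −5.00 D in METHODS but 2.00 to 5.00 D of myopia in CRITERIA FOR INCLUSION. Astigmatism is under 2.00 D in the former and under one dioptre in the latter. Reconcile also the control mean, 0.43 D against 0.45 D.
2. State in METHODS that the reconciled limits will be applied, before analysis, to the individual control records wherever the variable was recorded. Use the n, mean and SD of the qualifying controls in the comparison.
3. Report the source study's own criteria, how many of the 114 were dropped, and which limits could not be checked.
4. If individual records are not available, report this as a limitation of the efficacy conclusion.
5. Treat the filter as a complement to matching or adjustment on age and baseline refraction, not a replacement.

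**Cost.** Wording, a data filter and fewer controls. Losing 20% (114 to 91) gives SE = √(0.50²/40 + 0.52²/91) = 0.096 D, about 3% above 0.093 D. The loss could be larger if the 2.00 D lower limit is the one that applies. As an illustration, losing half (57 left) gives √(0.50²/40 + 0.52²/57) = 0.105 D, about 13% higher. No child's care changes.
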